Study Protocol

Title:

Effects of Taurine Supplementation on Repetitive Sprint Performance and Exhaustion Time in College Students Under High-Temperature and High-Humidity Conditions

Protocol ID:

No. 2021A43

Date:

January 9, 2025

1. Background

High-temperature and high-humidity environments (defined as ambient temperature \geq 35°C and relative humidity \geq 60%) adversely affect sports performance by increasing the body's heat load and impairing thermoregulation. These conditions lead to earlier fatigue, reduced performance, and increased physiological strain. Recovery after exhaustion is critical in such conditions for enhancing subsequent performance.

Taurine, a sulfur-containing amino acid, has shown promise in enhancing sports performance, improving calcium regulation in muscles, reducing oxidative stress, and mitigating fatigue under extreme environmental conditions. Previous studies have highlighted taurine's benefits, but the effects of different taurine doses in repetitive sprint (RS) exercises after exhaustive exercise in high-temperature and high-humidity conditions remain unclear. This study aims to investigate these effects in college students.

2. Objectives

Primary Objective:

To examine the effects of acute pre-exercise taurine supplementation at different doses (6g, 4g, 1g) on RS performance and endurance following exhaustive exercise in high-temperature and high-humidity environments.

Secondary Objectives:

- To analyze the impact of taurine on physiological indicators, such as heart rate (HR) and blood lactate (BLA).
- To measure subjective sensations using the rating of perceived exertion (RPE).
- To evaluate recovery performance through reverse vertical jump height.

3. Study Design

Design:

- Single-blind, randomized, crossover-controlled experimental design.
- Four groups: High-dose taurine (6g), Medium-dose taurine (4g), Low-dose taurine (1g), Placebo (0g).
- Each subject participated in four trials, one for each group.

Environment:

• Temperature maintained at 32±1°C and relative humidity ≥60%, using a heating system (SAWO, Finland) and humidification system (BELIN, China).

Participants:

- 16 college students (8 male, 8 female) from Capital University of Physical Education and Sports.
- Inclusion Criteria:
 - 1. Aged 18–28 years.
 - 2. No exercise-related risk as indicated by the PAR-Q questionnaire.
 - 3. No taurine-based supplementation in the past month.

Experimental Process:

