- Pre-exercise taurine/placebo ingestion (6g, 4g, 1g, or placebo).
- RS test (6 sprints, 10 seconds each, with 10-second recovery intervals).
- Measurements: Peak Power (PP), Mean Power (MP), Fatigue Index (FI), HR, BLA, RPE, and exhaustion time (ET).

4. Experimental Procedure

- 1. Warm-Up:
 - o 5-minute steady-state cycling at 100W.
 - o Measurement of reverse vertical jump height.
- 2. Exhaustive Exercise Test:

- Cycling test to exhaustion, starting at 50W and increasing by 50W every 3 minutes at 60 RPM.
- Exhaustion determined by cadence drop or inability to maintain resistance.

3. Rest and Recovery:

 20-minute recovery period with periodic measurements of HR, RPE, and BLA.

4. Repetitive Sprint Test (RS):

 Six maximal sprints (10 seconds each) with resistance set at 7.5% of body weight.

5. Measurements

- Sports Performance Indicators: PP, MP, FI (recorded for each sprint).
- Endurance and Recovery Indicators: ET, reverse vertical jump height.
- **Physiological Indicators**: HR and BLA (monitored pre-, post-exercise, and during recovery).
- **Subjective Indicators**: RPE assessed at pre-defined intervals.

6. Statistical Analysis

- Data analyzed using SPSS 27.0.
- Normality tested using the Shapiro-Wilk test.
- Repeated measures ANOVA (group × time) for performance indicators.
- Paired-samples t-tests for pre- and post-test comparisons.
- Significance level set at P<0.05.

7. Ethical Considerations

- Study approved by the Institutional Ethical Committee of Capital University of Physical Education and Sports, Beijing, China (No. 2021A43).
- Informed consent obtained from all participants.

Statistical Analysis Plan

Title:

Statistical Analysis Plan for the Effects of Taurine Supplementation on RS Performance in High-Temperature and High-Humidity Environments

Protocol ID:

No. 2021A43

Date:

January 9, 2025

1. Objectives

- Analyze the effects of different taurine doses on RS performance metrics (PP, MP, FI).
- Assess endurance and recovery indicators (ET, reverse vertical jump height).
- Investigate physiological responses (HR, BLA) and subjective fatigue (RPE).

2. Statistical Software

• SPSS Version 27.0.

3. Data Analysis Methods

- 1. Descriptive Statistics:
 - \circ Means \pm standard deviations calculated for all variables.
- 2. Normality Test:
 - Shapiro-Wilk test to check for normal distribution.
- 3. Primary Analysis:
 - Repeated measures ANOVA for group × time interaction effects on PP, MP, FI, HR, BLA, and RPE.

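### The planned repeated measures ANOVA has no rule for incomplete data; fitted within-subject, one missing sprint would drop that person from that outcome's model at every dose

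*Combined protocol and SAP*

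**What the plan says.** Protocol section 3 describes a "Single-blind, randomized, crossover-controlled experimental design" in "16 college students (8 male, 8 female) from Capital University of Physical Education and Sports", and adds: "Each subject participated in four trials, one for each group". The sprint test is specified as "RS test (6 sprints, 10 seconds each, with 10-second recovery intervals", and protocol section 5 lists "PP, MP, FI (recorded for each sprint" among the performance measures. In protocol section 4 the sprints come after a cycling test to exhaustion and a 20-minute recovery, at the resistance given in step 4: "Six maximal sprints (10 seconds each) with resistance set at 7.5% of body weight".

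For the analysis, protocol section 6 states "Data analyzed using SPSS 27.0", and SAP section 3, item 3 names the primary method: "Repeated measures ANOVA for group × time interaction effects on PP, MP, FI, HR, BLA, and RPE". Effect sizes are to be reported as partial eta-squared.

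The SPSS procedure is not named, and neither document says whether group enters as a within-subject factor. Neither contains a missing-data rule, an analysis-set definition, a dropout allowance, or a rule for an unfinished sprint or session.

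**The concern.** A classical repeated measures ANOVA with two within-subject factors works on one row per person with every cell filled. In the SPSS general linear model procedure for repeated measures, a person with any empty cell is left out of that model. Because the plan is silent, the software default would decide who is analysed.

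Two things would be at stake. The first is precision: with 16 people, each deletion also discards many values that were observed. The second is selection. The sprints follow exhaustive exercise in heat and humidity, and the protocol's background section itself expects earlier fatigue in such conditions. If sprints go unfinished because of fatigue, the people retained are those who coped under every condition. If dose affects who finishes, which is possible given the protocol's rationale that taurine mitigates fatigue, the dose comparison itself could be biased.

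**Working it through.** The documents give no power calculation, target effect, SD or expected loss, so there is no planned figure to reproduce. All loss rates below are assumptions.

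**Inputs from the documents:** 16 participants, 4 sessions each, 6 sprints per session.

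**Step 1. Cells.** 4 × 6 = 24 cells per person for each sprint outcome, and 16 × 24 = 384 in all. One missing sprint discards 24 − 1 = 23 observed values. One missing session discards 24 − 6 = 18. Deletion is per outcome: a lost lactate value does not remove a person from the peak power model.

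**Step 2. Participants left, assuming independent loss.** Expected complete cases are 16 × (1 − q)^4 for session loss q, or 16 × (1 − s)^24 for sprint loss s.

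| Assumed loss | Probability complete | Expected complete of 16 |
|---|---|---|
| 2% of sessions | 0.98^4 = 0.922 | 14.8 |
| 5% of sessions | 0.95^4 = 0.815 | 13.0 |
| 10% of sessions | 0.90^4 = 0.656 | 10.5 |
| 0.5% of sprints | 0.995^24 = 0.887 | 14.2 |
| 1% of sprints | 0.99^24 = 0.786 | 12.6 |
| 2% of sprints | 0.98^24 = 0.616 | 9.9 |

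Independence is the pessimistic case. One percent of 384 cells is about 3.8. If these fall as two late sprints in each affected session, about two people are affected and about 14 remain, not 12.6.

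**Step 3. Sessions used.** At 5% loss, 64 × 0.95 = 60.8 sessions are observed, and listwise deletion keeps 4 × 13.03 = 52.1. At 10% loss the figures are 57.6 and 4 × 10.50 = 42.0.

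**Step 4. Avoidable loss of precision.** The fair comparison is with a model that uses every observed session, not with complete data. This was simulated (4,000 replicates, one value per session, between-person SD 1.0, within-person SD 0.6, loss completely at random).

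| Session loss | SE, listwise | SE, all available data | Variance ratio | SE ratio |
|---|---|---|---|---|
| 5% | 0.238 | 0.221 | 1.16 | √1.16 = 1.08 |
| 10% | 0.263 | 0.227 | 1.34 | √1.34 = 1.16 |

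Both estimates rest on within-person differences, so these ratios do not depend on the SDs chosen. With no loss the SE would be 0.6 × √(2/16) = 0.212. The all-data model is therefore itself 0.221/0.212 = 1.04 or 0.227/0.212 = 1.07 times that, and no analysis recovers this part.

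**Step 5. Power, for scale.** Suppose power for the dose main effect were 80% at 16 people (assumption; noncentral F with sphericity). It would be 77% at 15, 69% at 13 and 55% at 10. For dose × sprint the figures are 76%, 68% and 52%.

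**Step 6. Selection.** In a second simulation weaker participants were assumed to miss more sessions. The completers then averaged 0.15 SD (5% loss) to 0.28 SD (10% loss) above the randomised group. This loss acted at person level only. Loss that depends on dose was not modelled, so these figures do not measure bias in a dose contrast.

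**The case against.** The strongest reply is that nothing has been shown to be missing. The protocol's past-tense statement that each subject took part in four trials suggests that all visits happened, which weakens the session-loss scenarios. That point stands. It does not show that every sprint was finished or every reading captured, so the risk lies mainly there. Even so, fatigue in a 10-second timed sprint ordinarily produces a low power value rather than an empty cell. The exhaustion criterion in protocol section 4 belongs to the preceding ride, not to the sprints. Losing one participant would cost only about 3 to 4 percentage points of power under the assumed baseline.

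A reader might also infer that the plan states a deletion rule. It does not. Listwise deletion follows from the method and the software, and partial eta-squared reporting fits that procedure, but the procedure is unnamed. The SAP's one-way ANOVA across groups for exhaustion time leaves open that group might be entered as a between-subject factor. A missing sprint would then remove one person-session rather than all four doses, but the within-person pairing would be ignored, which is a different and larger error in a crossover.

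A reader might further take the full rise in standard error against complete data, 0.95^−2 = 1.11 or 0.90^−2 = 1.23, as what a better model would save. Step 4 shows that only about 8% or 16% is avoidable.

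**Conclusion.** The gap is real and cheap to close, but it is conditional. On the reading that fits the crossover, with dose and sprint both within-subject, one empty cell removes a person from that outcome's model at every dose, and nothing in the protocol or SAP prevents this. Under assumed random session loss of 5% or 10%, the avoidable inflation of the standard error of a dose contrast is about 8% or 16%.

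Two stronger readings are not supported. The documents do not show that participants have been lost. Nor do they show that deletion would remove exactly the most fatigued people: it would do so disproportionately, and only if loss is related to fatigue. A mixed model should not be taken as a cure for that second problem either. It is valid when loss is at random given the observed data, and not when stopping depends on the sprint result that was never seen.

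**What to change.** Replace the ANOVA in SAP section 3, item 3 with a linear mixed model (SPSS MIXED) fitted to all observed values:

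- **Fixed effects:** dose, visit, sprint or time point, and dose × time.
- **Random effects:** participant, participant-by-visit and participant-by-sprint (or time point), or a suitable within-visit covariance structure in place of these. The participant-by-sprint term matters. Without it the error for dose × time pools 5 × 15 = 75 and 15 × 15 = 225 degrees of freedom, where the within-subject ANOVA uses 225, and the planned test would not be matched.
- **Estimation:** REML with small-sample degrees of freedom.
- **Reporting:** incomplete sprints and sessions by dose, with reasons.
- **Sensitivity analysis:** if any sprint was stopped because of fatigue, examine how the dose comparison changes when the unseen values are assumed worse than the model predicts.

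If data already exist, state completeness by dose and sprint and label the change of model as made after data collection.

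The cost is SAP wording, somewhat more modelling work and an explicit covariance assumption, in the same software. With complete, balanced data the result should be close to that of the within-subject ANOVA.

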- 4. Secondary Analysis:
 - Paired-samples t-tests for reverse vertical jump pre- and post-exercise comparisons.

o One-way ANOVA for ET across groups.

5. Effect Sizes:

o Partial eta-squared (η^2 partial): 0.01 (small), 0.06 (medium), 0.14 (large).

4. Data Presentation

- Line graphs for repeated measures (PP, MP, FI, HR, BLA, RPE).
- Bar charts for pre- and post-test comparisons (reverse vertical jump).

5. Significance Criteria

• Statistical significance set at P<0.05.

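### Reverse vertical jump is tested only before versus after exercise; no planned test compares it between the taurine doses and placebo

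*Combined protocol and SAP*

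**What the plan says.** SAP section 3 plans three inferential procedures:

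- Item 3, primary: "Repeated measures ANOVA for group × time interaction effects on PP, MP, FI, HR, BLA, and RPE". Jump is not in the list.
- Item 4, secondary: "Paired-samples t-tests for reverse vertical jump pre- and post-exercise comparisons".
- Item 4, secondary: "One-way ANOVA for ET across groups", where ET is exhaustion time.

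Item 1 adds means and "standard deviations calculated for all variables", which is description. SAP section 4 plans to show jump only as before/after bar charts.

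Protocol section 6 is less specific: "Repeated measures ANOVA (group × time) for performance indicators" and "Paired-samples t-tests for pre- and post-test comparisons".

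Jump height is the measure for a secondary objective on recovery (Protocol section 2). SAP section 1 puts it on the same line as ET: "Assess endurance and recovery indicators (ET, reverse vertical jump height" and so on. Under Protocol section 3, each of the 16 participants completes one trial on each of 6 g, 4 g, 1 g and placebo.

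**The concern.** A before/after t-test estimates the effect of the exercise bout on jump height. It does not estimate the difference between a dose and placebo, which is the contrast the randomised crossover exists to provide. The SAP does not say whether the t-test is pooled over conditions or run separately in each, but neither version compares conditions.

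Two misreadings are then open to whoever reports the trial. A pooled result could be presented as a finding about taurine when it contains no information on dose. Four separate P values could be read against each other, so that a significant fall on placebo and a non-significant fall on one dose is taken as a benefit. That pattern is not a test of the difference between the two conditions.

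**Working it through.** **Step 1: match each listed outcome to its planned tests.** This step alone settles the point.

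| Outcome | Planned test across conditions | Other planned test |
|---|---|---|
| PP, MP, FI | group × time ANOVA | none |
| HR, BLA, RPE | group × time ANOVA | none |
| ET | one-way ANOVA | none |
| Reverse vertical jump | **none** | paired t-test, before/after |

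The count is 6 + 1 = 7 of 8 outcomes with a test across conditions. Whether one-way ANOVA suits a crossover is a separate matter.

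**Step 2: does the looser wording of Protocol section 6 bring jump in?** Protocol section 5 gives the performance label to PP, MP and FI, and places jump with ET in a separate endurance and recovery class. The SAP then names its six ANOVA variables and leaves jump out. Neither document supports the wider reading.

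**Step 3: illustration of the consequence.** The plan states no SD, expected fall, correlation or power, so there is no figure of its own to reproduce. From the documents: n = 16, four conditions, significance level 0.05. Assumed: two-sided testing, normal change scores with SD 1, and equal correlation ρ from 0 to 0.9 between a participant's changes in different conditions. The condition × time test is a one-way repeated-measures ANOVA on change scores, with 4 − 1 = 3 and 3 × 15 = 45 degrees of freedom. Ranges run over ρ; simulated values use 100,000 trials per cell unless noted.

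*Pooled over conditions (participant means):*

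| Scenario | Mean fall | Pooled t-test significant | Condition × time rejects |
|---|---|---|---|
| 0.75 SD in all four (no taurine effect) | 0.75 | 83–100% | 5% |
| 1.5 SD on placebo, 0.5 SD on each dose | (1.5 + 3 × 0.5)/4 = 0.75 | 83–100% | 80–100% |

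The pooled test cannot separate the two rows, because it depends only on the mean fall and the covariance, which are the same in both.

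*Run within each condition, large falls:*

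| Scenario | Mean fall | All four t-tests significant | Condition × time rejects |
|---|---|---|---|
| 1.5 SD on placebo, 1.0 SD on each dose | (1.5 + 3 × 1.0)/4 = 1.125 | 89–94% | 25–99.7% |
| 1.125 SD in all four (no taurine effect) | 1.125 | 95–98% | 5% |

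*Run within each condition, moderate falls, no taurine effect.* If each test has power p and the tests are independent, at least one dose disagrees with placebo on significance with probability 1 − p⁴ − (1 − p)⁴:

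- p = 0.5 (fall of 0.52 SD): 1 − 0.0625 − 0.0625 = 87.5%
- p = 0.8 (fall of 0.75 SD): 1 − 0.4096 − 0.0016 = 58.9%

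Correlation lowers these figures. In smaller simulations (20,000 to 40,000 trials per cell) they fall to about 28% and 19% at ρ = 0.9. A direct paired test of dose against placebo rejects about 5% of the time per contrast.

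**Step 4: precision of the missing comparison.** The 95% confidence half-width for one dose minus placebo, in SDs of the change score, is t(15, 0.975) × √(2(1 − ρ))/√16, with t = 2.131:

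- ρ = 0: 2.131 × 1.414/4 = 0.75
- ρ = 0.5: 2.131 × 1.000/4 = 0.53
- ρ = 0.7: 2.131 × 0.775/4 = 0.41
- ρ = 0.9: 2.131 × 0.447/4 = 0.24

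**The case against.** The strongest reply is that the plan never promises a dose comparison for jump. The primary objective and the HR/BLA objective name taurine; the jump objective does not, and the SAP's line on jump speaks only of assessing it. A before/after test with a before/after chart fits that literal wording. It is true that the comparative purpose is inferred. The inference is nevertheless well supported: the RPE objective does not name taurine either, yet RPE gets a group × time test; ET shares jump's line in the SAP objectives and is tested across groups; and the design is placebo-controlled throughout.

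Three further objections stand in part.

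- **Importance.** Jump is a secondary outcome, and the primary-objective outcomes are untouched. This limits the weight of the point but does not remove it.
- **A more basic gap.** Protocol section 4 lists jump only at warm-up, and its recovery step lists HR, RPE and BLA. Without post-exercise jumps, both the planned t-test and the added comparison are moot.
- **The illustration.** Its inputs are assumed, and the pooled result follows by construction. With large falls the separate tests look nearly uninformative; with the moderate falls of the pooled table they are less so, with all four significant in about 41–70% of trials under no effect against 10–35% under benefit. The added test may also be inconclusive: for a 0.5 SD benefit it rejects in only 25–48% of trials at ρ from 0 to 0.5.

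None of this supplies the missing test.

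**Conclusion.** The concern holds. Jump is the one listed outcome of eight with no planned test across conditions, so the plan offers no inferential basis for saying that taurine did or did not change jump height. This rests on the text of the two plans and needs none of the simulated figures, whose SDs, falls and correlations are assumptions. Descriptive statements by condition remain possible if the means and SDs are tabulated that way. It should be fixed, at the weight of a secondary outcome. With 16 participants the added comparison may be imprecise unless a participant's changes are highly correlated across conditions.

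**What to change.** 1. Define the post-exercise jump: after exhaustion, after the 20-minute rest, or after the sprints. Reconcile this with Protocol section 4.
2. State whether the warm-up jump comes before or after ingestion. Protocol section 3 lists ingestion first, so it may be a post-dose value.
3. Add jump to the within-subject comparison of conditions.
   - If the warm-up jump is pre-dose, use at minimum the condition × time term of a 4 × 2 repeated-measures ANOVA. A mixed model with participant, condition and period, with the warm-up jump as a possible covariate, is an alternative.
   - If it is post-dose, taurine may already have affected it, and adjusting for it could remove part of the effect. Make the unadjusted comparison of post-exercise jump across conditions the main analysis, and the change or adjusted analysis secondary.
4. Report each dose minus placebo with a 95% confidence interval and a stated multiplicity rule. The plan sets no such rule for any outcome, so that gap is not specific to jump.
5. Keep the before/after t-tests as descriptive.
6. If results have already been seen, label the added analysis post hoc.

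If the sponsor truly wants only a before/after question for jump, the SAP should say that jump is descriptive and will support no claim about taurine.

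The cost is a few lines of SAP text and a little more analysis. No data are needed beyond the post-exercise jumps that the planned t-test already requires, provided they exist for all four trials.

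### The SAP tests a post-exercise jump whose timing is stated nowhere, and its paired pre/post test does not compare taurine with placebo.

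*Combined protocol and SAP*

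**What the plan says.** Protocol Section 2 gives a secondary objective: "To evaluate recovery performance through reverse vertical jump height". Section 5 classes the jump with exhaustion time: "Endurance and Recovery Indicators: ET, reverse vertical jump height".

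The four-step procedure in Section 4 mentions the jump once, under step 1 (Warm-Up): "Measurement of reverse vertical jump height". Step 2, the exhaustive test, names no jump. Step 3 reads "20-minute recovery period with periodic measurements of HR, RPE, and BLA". Step 4 reads "Six maximal sprints (10 seconds each) with resistance set at 7.5% of body weight". The measurement list under Experimental Process in Section 3 does not include the jump: "Measurements: Peak Power (PP), Mean Power (MP), Fatigue Index (FI), HR, BLA, RPE, and exhaustion time (ET").

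SAP 3.4 (Secondary Analysis) plans "Paired-samples t-tests for reverse vertical jump pre- and post-exercise comparisons", and SAP Section 4 plans "Bar charts for pre- and post-test comparisons (reverse vertical jump"). The group × time ANOVA in SAP 3.3 covers PP, MP, FI, HR, BLA and RPE, but not the jump.

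**The concern.** The analysis needs two jump values per session, and the procedure gives a time for only one. The SAP calls the second value post-exercise, but a session contains two exercise tests with a rest between them, so the term does not identify one moment. The possible moments measure different things. If the choice is left to whoever runs the session, the interval since exhaustion may vary from visit to visit. A jump that was not taken, or was taken at an unrecorded time, cannot be recovered by analysis.

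A second gap lies in the same SAP line. The trial asks whether taurine at three doses changes outcomes relative to placebo. A paired test of before against after shows whether the session changed jump height, which is a different question. As planned, the recovery objective would be reported without any test of taurine.

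**Working it through.** No figure is stated for the jump, so there is none to reproduce. The check sets the schedule beside the analysis, then asks what the planned test estimates.

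**1. Where the jump is timed**

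| Place | Jump mentioned? | Time given? |
|---|---|---|
| Protocol 2, secondary objective | Yes, as the recovery measure | No |
| Protocol 3, Experimental Process list | No | – |
| Protocol 4, step 1 (warm-up) | Yes | Before the exhaustive test |
| Protocol 4, steps 2, 3 and 4 | No | – |
| Protocol 5 | Yes, as an endurance/recovery indicator | No (HR and BLA do get pre, post and recovery timing) |
| Protocol 6 | Not named; paired pre/post tests only | No |
| SAP 1 | Yes, as an endurance/recovery indicator | No |
| SAP 3.4 and SAP 4 | Yes, pre and post | The post moment is not defined |

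**2. What the later jump could be**

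- *Straight after exhaustion:* acute fatigue from the incremental test.
- *After the 20-minute rest:* recovery from that test.
- *After the sprints:* recovery plus sprint fatigue.

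The first two are 20 minutes apart. Between the second and third come 6 × 10 s = 60 s of maximal sprinting and 5 × 10 s = 50 s of intervals, 110 s in all (sprint and interval lengths from Experimental Process).

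**3. How many values are involved**

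- Sessions: 16 participants × 4 trials = 64.
- Jumps with a stated time: 64 × 1 = 64, all before the exhaustive test.
- Later jumps with a stated time: 0.
- With one later jump at a defined time in each session: up to 16 pairs per condition and 16 × 4 = 64 pairs in total, if none are missing.

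**4. What the paired test estimates**

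For condition *d* (6 g, 4 g, 1 g or placebo), let Δ(d) = mean of (post − pre). A paired t-test run by condition tests Δ(d) = 0. Pooled over conditions, it tests whether the average of the four Δ values is 0. The SAP does not say which is meant. The treatment question is whether Δ(d) − Δ(placebo) = 0, and neither version tests it. Finding Δ significant for one dose and not for placebo would not be a test of that difference either.

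**The case against.** The strongest reply is that Section 4 is a summary and should be read with the rest of the document. It also leaves out taurine or placebo ingestion, which appears only under Experimental Process, and it does not list the recording of PP, MP, FI or exhaustion time. Step 1 lists no HR or BLA, although Section 5 wants both before exercise. The Experimental Process list omits the jump even though step 1 includes it. Neither list is complete, and the SAP's test and bar chart show that a later jump was intended.

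This reply stands against a stronger reading. From the count above, a reader might infer that none of the 64 sessions would yield a post-exercise jump, and that the recovery objective cannot be answered. The documents do not support that: an omission from an incomplete list does not show that the measurement was not made. The reply does not supply the missing time, however, and intent alone cannot choose among the three moments.

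A reader might also infer that variable timing confounds recovery time with dose. In a randomized crossover, that requires timing to differ systematically by dose, and nothing in the documents says it does. Unrelated variation adds noise, which still matters with 16 participants. The possibility of bias stays open because the design is single-blind without saying who is blinded.

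Finally, the choice of time point belongs to the sponsor. No text limits recovery performance to the interval before the sprints, and a jump placed just before them could affect PP, MP and FI.

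**Conclusion.** The point holds as a mismatch between procedure and SAP, together with an analysis that does not address the treatment question. The post-exercise jump is intended but has no stated time, and its three plausible readings are different quantities. Once the time is settled, the paired pre/post test still contains no contrast between taurine and placebo, and no other listed analysis provides one for the jump.

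The reach is limited to one secondary objective, although the jump is the only measure that the objectives name for recovery. The primary analysis is not affected. How much precision is lost through variable timing cannot be calculated, because the documents give neither the variability of jump height nor the actual timing.

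The conclusion assumes that the four-step list and the SAP line are complete as printed; there is no sign of redaction or a missing figure there. It does not assume that the later jump was never taken.

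**What to change.** 1. **Reconcile protocol Section 4 with SAP 3.4.** State one time for the post-exercise jump, the same at every visit, and define the SAP term as that measurement. The end of the 20-minute rest best matches the recovery objective. Before adopting it, the sponsor should confirm that a jump there does not disturb the sprint outcomes.
2. **If sessions are already complete** (some protocol statements are in the past tense, which suggests this without proving it), state when the later jump was actually taken, or that it was not, and define the SAP term accordingly.
3. **In SAP 3.4, replace the stand-alone paired t-tests** with a within-participant comparison between doses. This can be a dose × time repeated-measures analysis, or the post-exercise jump compared between doses accounting for that visit's warm-up jump. State whether the warm-up jump follows ingestion, since Section 4 does not place the dose. If it does, the warm-up value may already carry a taurine effect, and adjusting for it would narrow the question to the later change.

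The cost is at most one repeat of an existing measurement per session (64 in all), a few lines of wording in each document, and a small change to the analysis.

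### Exhaustion time is assigned a one-way ANOVA for independent groups, although the same 16 students supply all four dose values; with positive within-person correlation the test is conservative and gives up the crossover's power

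*Combined protocol and SAP*

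**What the plan says.** Protocol section 3 gives the design as "Single-blind, randomized, crossover-controlled experimental design". It has four conditions (taurine 6 g, 4 g and 1 g, and placebo) and adds: "Each subject participated in four trials, one for each group". The sample is "16 college students (8 male, 8 female) from Capital University of Physical Education and Sports".

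SAP section 3 assigns the tests:

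- Item 3 (primary): "Repeated measures ANOVA for group × time interaction effects on PP, MP, FI, HR, BLA, and RPE".
- Item 4 (secondary): paired t-tests for jump height before and after exercise, and for exhaustion time "One-way ANOVA for ET across groups".
- Item 5: partial eta-squared, with 0.01, 0.06 and 0.14 as small, medium and large.

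No participant term is attached to the ET test anywhere. Protocol section 6 does not supply one. Its repeated-measures line covers performance indicators, whereas section 5 puts ET under endurance and recovery ("ET, reverse vertical jump height").

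**The concern.** The test usually called one-way ANOVA assumes that the four sets of values come from different people. Here they come from the same 16. Between-person variation cancels from every difference between dose means, because each student contributes to all four, yet the one-way test still counts that variation as error. Much of it is likely to be large: the sample is half male and half female, and the exhaustion test raises the load in fixed 50 W steps whatever the person's size or fitness.

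Exhaustion time is in the study title, and endurance is named in the protocol's primary objective, although the SAP lists ET as secondary. The danger is a non-significant ET result that reflects the choice of test and not the absence of a dose effect. The effect size would also be on a different scale from that of the outcomes analysed by repeated measures.

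**Working it through.** The documents contain no sample-size or power calculation, so there is no planned figure to reproduce. The check compares the two tests under stated assumptions.

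**Inputs from the documents.** n = 16 people, k = 4 doses (0, 1, 4, 6 g), alpha 0.05.

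**Assumptions.** Total SD of ET set to 1; within-person correlation (ICC) ρ = 0.3, 0.5 or 0.8, equal for all pairs of doses; dose effect linear in grams with size d (in total SDs) at 6 g; no period or carry-over effect.

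**Step 1: the two F tests.**
- One-way: error df = 4 × (16 − 1) = 60; critical F(3,60) = 2.758.
- Within-subject: error df = (16 − 1) × (4 − 1) = 45; critical F(3,45) = 2.812.

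**Step 2: the error term.** The within-subject error has expectation 1 − ρ. The one-way error pools it with the participant sum of squares, so its expectation is [45(1 − ρ) + 15(1 + 3ρ)]/60 = 1. The true variance of a difference between two dose means is 2(1 − ρ)/16, but the one-way test works with 2/16. Its standard error is therefore too large by 1/√(1 − ρ): 1.2, 1.4 and 2.2 times at ρ = 0.3, 0.5 and 0.8.

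**Step 3: type I error of the one-way test** (nominal 5%, simulated): about 1.4% at ρ = 0.3, 0.3% at 0.5 and 0.002% at 0.8. The within-subject test stays at 5%.

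**Step 4: power.** The dose means are 0, d/6, 4d/6 and d, with variance v = 0.158d². The within-subject noncentrality is 16 × 4 × 0.158d²/(1 − ρ) = 10.11d²/(1 − ρ). For d = 0.5 and ρ = 0.5 this is 10.11 × 0.25/0.5 = 5.06, which gives 41% power. One-way power was simulated. Total-scale eta-squared is v/(v + 1).

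| d (SD) | Total-scale eta-squared | ρ = 0.3: one-way vs within | ρ = 0.5 | ρ = 0.8 |
|---|---|---|---|---|
| 0.3 | 0.01 | 5 vs 13% | 2 vs 17% | 0.2 vs 37% |
| 0.5 | 0.04 | 15 vs 30% | 10 vs 41% | 3 vs 83% |
| 0.8 | 0.09 | 48 vs 68% | 44 vs 84% | 37 vs >99% |
| 1.0 | 0.14 | 73 vs 88% | 73 vs 96% | 74 vs >99% |

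At ρ = 0 and d = 0.5 the figures are 22.2 vs 21.8%.

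The smallest effect with 80% power is about 1.05 SD for the one-way test at each of these correlations. For the within-subject test it is 0.91, 0.77 and 0.49 SD.

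**Step 5: effect size.** A partial eta-squared of 0.14 against within-person error means f² = 0.14/0.86 = 0.163. On the one-way scale f² becomes 0.163(1 − ρ), and eta-squared = f²/(1 + f²) is 0.102, 0.075 and 0.032 at ρ = 0.3, 0.5 and 0.8. For an effect of that size the power is 54, 32 and 2% with the one-way test, against 74% throughout with the within-subject test.

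**Sensitivity to dose spacing.** With four equally spaced means and Cohen's f = 0.25 on the total SD, power is 26 vs 46% at ρ = 0.3, 21 vs 61% at 0.5 and 12 vs 96% at 0.8.

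**The case against.** The best defence is that one-way may simply mean one factor, with repeated measures understood. ET has a single value per trial, so it could not appear in a list of dose-by-time analyses, and its absence from that list does not show that independent groups were intended. That much is right. What remains is the ordinary meaning of the test named and the lack of any participant term, while the same section names repeated-measures or paired methods for every other outcome. An analyst following the line literally would run the independent-groups test, so it needs rewording on either reading.

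It can also be said that the harm is limited. With positive correlation no false claim arises, ET is listed as secondary, and a large effect on the total-SD scale keeps about 74% power. All three are true. They restrict the damage to small and moderate effects, which are also the effects for which a study of 16 people most needs its crossover.

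The word conservative depends on positive correlation. At correlations of −0.1 and −0.2 the one-way test rejects 6.7% and 9.0% of the time under no effect. Negative correlation is implausible for ET in the same people.

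One-way eta-squared is not miscalculated. It is a valid quantity on the total-variance scale, and the SAP does not say which scale its benchmarks refer to. The shrinkage matters only if they are read against within-person error, as for partial eta-squared from a repeated-measures model.

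**Conclusion.** The concern holds. The ET test as named does not fit the documented design and should be corrected before ET is analysed. For any positive within-person correlation it is conservative, and for small and moderate effects its shortfall in power against the within-subject test grows with that correlation. For large effects the gap levels off near 25 percentage points, only because the within-subject test reaches its ceiling.

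The direction follows from the design alone. The size rests on the assumed correlation, effect and equal-correlation structure, none of which the documents give. At 0.5 SD the loss runs from about 15 percentage points (correlation 0.3) to about 80 (correlation 0.8).

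**What to change.** Replace the ET line in SAP section 3, item 4 with one of these:

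- a one-factor repeated-measures ANOVA on dose (0, 1, 4, 6 g) with a Greenhouse-Geisser correction; or
- a linear mixed model with participant as random effect and dose as a within-participant fixed effect.

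State that partial eta-squared for ET comes from this model.

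Two additions are useful but not needed to cure the defect: visit number (period 1–4) as a fixed effect, and each dose minus placebo with a 95% confidence interval and Holm-adjusted P values.

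The cost is wording, with no new data. Error df fall from 60 to 45, and to 42 with the period term. The sphericity correction is cheap. In a check with within-person SDs in the ratio 1, 1, 1.5, 2 (epsilon 0.81), the uncorrected test rejected 6.3–6.5% under no effect and the corrected one 4.4–4.5%.

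The protocol describes the trials in the past tense, and the documents do not settle whether ET data had been collected or seen when the SAP was dated. If they had, record the change with its date and give the crossover design as the reason.
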